4 STUDY DESIGN

4.1 Overall Design

4.1.1 Hypothesis

The hypothesis of this study is that addition of TTFIELDS treatment to adjuvant temozolomide will significantly increase OS in patients with newly diagnosed Grade II and III astrocytoma with TERT promoter mutation only compared to historical and contemporaneous controls.

4.1.2 Description

This is a phase 2, multi-institutional, open-label, historically controlled, study of 100 patients with newly diagnosed high-risk Grade II and III astrocytoma combining TTFIELDS with adjuvant temozolomide compared to historical and contemporaneous controls after the completion of definitive chemoradiotherapy. The primary endpoint will be overall survival. This high-risk astrocytoma subgroup constitutes approximately 10% of all Grade II and III gliomas (Fig. 6). Therefore, in order to achieve targeted accrual goals, this study is being conducted in a consortium of 10-20 high volume brain tumor centers in the U.S.

[figure not shown]

Figure 6 Prevalence of TERT Promoter Mutation in Grade II and III Glioma. (Adapted from Eckel-Passow JE et al. *N Engl J Med* 2015;372: 2499-2508).

4.1.3 The 2016 World Health Organization (WHO) Classification of Grade II and III gliomas

This new classification provides extensive updates to the previous version from 2007 [77]. For WHO grade II and III gliomas, astrocytomas are now defined by the absence of 1p19q codeletions as determined by FISH, while oligodendrogliomas are defined by the presence of 1p19q codeletions AND IDH1/2 mutation as determined by next generation sequencing (NGS). The concordance rate between 1p19q codeletions and IDH1/2 mutation is extremely high. Gliomas with 1p19q codeletions and without IDH1/2 mutation represents an exceedingly rare entity. In fact, in the Eckel-Passow et al. study, of the 1087 infiltrating gliomas, Pisapia found no case with whole arm 1p19q codeletions was associated with wild-type IDH1/2 [18, 78]. Even when partial arm deletions were included, only 0.3% of cases with partial deletions of 1p19q was without IDH1/2 mutation [18, 78]. In fact, per WHO guidelines, oligodendrogliomas should not be diagnosed in the absence of IDH1/2 mutation (and/or 1p19q codeletions) regardless of histologic appearance since the lack of IDH1/2 mutation is equivalent to the absence of 1p19q codeletions. Thus, the absence of IDH1/2 mutation is mutually exclusive of 1p19q codeletions in the vast majority of cases. Therefore, for the purpose of this study, WHO grade II and III gliomas without IDH1/2 mutation as determined by NGS (rare variants of unknown significance are excluded and not considered to be pathologic mutations) will be considered to also have intact 1p19q (i.e. without codeletions) and a FISH test to determine 1p19q codeletions status will not be required.

4.1.4 Study Sites

A complete list of study sites will be maintained by the Coordinating Center.

4.2 Scientific Rationale for Study Design

See section entitled Study Rationale.

4.3 Justification for Dose

4.3.1 Temozolomide

Dosing instructions are consistent with the usage guidelines for refractory anaplastic astrocytoma listed in the package insert. See package insert for full details.

4.3.2 Optune

Usage instructions are consistent with the usage guidelines approved for Optune by FDA for GBM.

4.4 End of Study Definition

A participant is considered to have completed the study if he or she withdraws consent, is withdrawn by the investigator, is declared lost to follow-up, or dies.

5 STUDY POPULATION

5.1 Inclusion Criteria

In order to be eligible to participate in this study, an individual must meet all of the following criteria:

- A. Willing and able to provide written informed consent
- B. Stated willingness to comply with all study procedures and availability for the duration of the study
- C. Male or female, 18 years or older
- D. Life expectancy of at least 3 months
- E. Histologic confirmation of WHO Grade II or III astrocytoma
 - a. mixed oligoastrocytomas are permitted
- F. Mutational identity determined by CLIA-certified sequencing including:
 - a. IDH1/2 wildtype (i.e. lack of detectable mutations on the sequencing report, variants of unknown significance or non-synonymous single nucleotide polymorphisms deviating from wild-type sequence do not apply)
AND
 - b. TERT promoter mutation(s)
- G. Karnofsky performance status $\geq 70\%$
- H. Maximal safe resection
 - a. biopsy alone is allowed
- I. Completed standard chemoradiation with total RT dose of at least 40 Gy and concurrent temozolomide (75mg/m² daily dose with 80% prescribed dose completed)
 - a. Patients with a tumor that was biopsied or resected in the past followed by observation only without definitive chemoradiation and/or chemotherapy given will be eligible, as long as: repeat maximal surgical resection (biopsy only allowed) has been performed, definitive temozolomide/RT treatment meets the criteria above, and adjuvant temozolomide treatment is planned
- J. Candidate for adjuvant high dose temozolomide per investigator's clinical judgement
- K. Adjuvant Temozolomide start date at least 4 weeks, but not more than 6 weeks, from the later of last dose of concomitant temozolomide or radiotherapy
- L. No evidence of early disease progression per RANO criteria at the time of enrollment
- M. Women of childbearing potential (WOCBP) must be using a highly effective method of contraception to

avoid pregnancy throughout the study and for at least 24 weeks after the last dose of study drug to minimize the risk of pregnancy.

- a. Prior to study enrollment, women of childbearing potential must be advised of the importance of avoiding pregnancy during trial participation and the potential risk factors for an unintentional pregnancy.
 - b. Refer to section 10.2.1 for guidance on highly effective contraceptive methods acceptable in this study.
 - c. WOCBP include any woman who has experienced menarche and who has not undergone successful surgical sterilization (hysterectomy, bilateral tubal ligation, or bilateral oophorectomy) or who is not post-menopausal. Post-menopause is defined as:
 - i. Amenorrhea that has lasted for ≥ 12 consecutive months without another cause, or
 - ii. For women with irregular menstrual periods who are taking hormone replacement therapy (HRT), a documented serum follicle-stimulating hormone (FSH) level of greater than 35 mIU/mL.
- N. Males with female partners of child-bearing potential must agree to use physician-approved contraceptive methods (e.g., abstinence, condoms, vasectomy) throughout the study and should avoid conceiving children for 24 weeks following the last dose of study drug.
- O. Patient must agree to wear the Optune device. If patient declines to wear the Optune device for personal and non-medical reasons (except for history of known allergy to hydrogel) and the plan is to treat the patient with adjuvant TMZ alone, the patient can be considered for enrollment in the contemporaneous control cohort (See Section 9, Control Cohort).

5.2 Exclusion Criteria

An individual who meets any of the following criteria will be excluded from participation in this study:

- A. Prior treatment with anti-angiogenic agents including bevacizumab.
- B. Prior treatment with TTFIELDS.
- C. Progressive disease (according to RANO criteria) after temozolomide/RT.
- D. Actively participating in another clinical treatment trial intended to treat the underlying astrocytoma.
- E. Females who are pregnant or breastfeeding.
- F. Significant co-morbidities at baseline (within 2 weeks prior to adjuvant temozolomide start) which would prevent adjuvant temozolomide treatment:
 - a. Thrombocytopenia (platelet count $< 100 \times 10^3/\mu\text{L}$)
 - b. Neutropenia (absolute neutrophil count $< 1.5 \times 10^3/\mu\text{L}$)
 - c. CTC grade 4 non-hematological toxicity (except for alopecia, nausea, vomiting)
 - d. Significant liver function impairment - AST or ALT > 5 times the upper limit of normal
 - e. Total bilirubin > 2 times upper limit of normal
 - f. Significant renal impairment (GFR ≤ 30 ml/min)
- G. Implanted pacemaker, programmable shunts, defibrillator, deep brain stimulator, other implanted electronic devices in the brain, or documented clinically significant arrhythmias.
- H. A skull defect such as missing bone with no replacement
- I. Bullet fragments embedded the skull
- J. Tumors located in the brain stem and/or the cerebellum.
- K. History of hypersensitivity reaction to temozolomide, Dacarbazine (DTIC) or hydrogel.

5.3 Additional Considerations

- Operable patients (biopsy alone allowed) must undergo surgery prior to enrollment.
- All patients must have received radiation therapy with concomitant temozolomide prior to enrollment.
- Patients receiving steroids to control edema may be included in the trial; however, any change in steroid dose must be documented during the follow-up visits.
- Disease status will be determined by comparing screening MRI to the immediate post-surgical MRI. If unavailable, an immediate post-surgical CT can be used for the same purpose.
- Patients who have progressive disease at screening (compared to the immediate post-surgical MRI) are not candidates for this study.
- In the case of local radiological suspicion of pseudoprogression, the patient is still eligible for the study per RANO criteria. However, other imaging modalities (e.g. brain PET, perfusion in addition to T1 weighted MRI) can be obtained to assess biological activity of the tumor if desired but not required by the study.

5.4 Screen Failures

Screen failures are defined as participants who consent to participate in the clinical trial but do not meet the criteria for participation in this trial. A minimal set of screen failure information is required to ensure transparent reporting of screen failure participants, to meet publishing requirements and to respond to queries from regulatory authorities. Minimal information includes demography, screen failure details and eligibility criteria.

Individuals who do not meet the criteria for participation in this trial (screen failure) may not be rescreened. Participants may repeat individual lab tests within the screening window, but no modifications to the screening window or I/E criteria are permitted. No protocol exceptions are permitted and no waivers will be granted for enrollment into this protocol.

This protocol estimates a 10% screen failure rate.

5.5 Strategies for Recruitment and Retention

Potentially eligible patients scheduled to undergo maximal surgical resection of a Grade II or III astrocytoma will be identified through direct referral at participant sites. PHI will be reviewed by the PI(s) and/or Study Coordinator but not recorded in order to pre-screen patients for eligibility for this trial. The pre-screening PHI will consist of a review of the medical records to confirm new diagnosis in adults age 18 years or older, as well as tumor cytogenetic and DNA sequencing characteristics (Mutational identity determined by CLIA-certified sequencing as possessing a IDH1/2 wildtype and TERT promoter mutated genotype).

Since high-risk astrocytomas are only approximately 10% of all Grade II and III gliomas, only those patients who have appropriate tumor characteristics after biopsy will be approached about the study. Potential subjects will be approached well in advance of study commencement to ensure sufficient time for review of the informed consent form and other logistical coordination.

Since the primary outcome of the study is overall survival, each patient's Legally Authorized Representative (LAR) will be recorded at enrollment. In the event that the subject loses capacity to consent for himself/herself during the course of the study, the LAR will be approached for the Survival Follow-up items (only) for that subject.

Information on this study will be posted on ClinicalTrials.gov. Recruitment is planned for 36 months in total.

5.5.1 Screening

- Patients with newly diagnosed high-risk Grade II or III astrocytoma must undergo maximal safe resection (biopsy alone may be eligible).
- Patients must undergo chemoradiotherapy: concomitant 75mg/m² daily temozolomide with 80% prescribed dose completed and RT with minimal RT dose of 40 Gy delivered.
- Within three weeks prior to beginning adjuvant temozolomide, all patients will undergo a Baseline contrast-enhanced MRI of the brain.
- Within two weeks prior to beginning adjuvant temozolomide, all patients will undergo the following assessments:
 - Medical History and demographics
 - Medication History
 - Steroid Dose (recorded)
 - MGMT methylation status (if feasible, required for stratification)
 - Tumor Tissue sample – verify availability of FFPE, pathology slides, and/or frozen sample(s)
 - RANO assessment
 - Complete physical examination
 - Neurological status and KPS
 - CBC with differential
 - Pregnancy test (urine or serum) – WOCBP only
 - Biochemistry panel (Electrolytes, creatinine, bilirubin, liver enzymes)
 - Quality of life questionnaires (EORTC QLQ-C30/BN20, and MMSE)

No study-specific procedures may be performed prior to obtaining informed consent. However, assessments performed according to standard of care, prior to consent, may be used to fulfill the screening requirement if they are part of the patient’s medical record within the specified timeframe.

See Section “Enrollment Documentation Requirements” for a complete list of patient enrollment documentation.

5.5.1.1 Mini-Mental Status Exam

The Mini-Mental Status Exam is a standardized tool to measure neurocognitive function. The MMSE is scored on a scale of 0 to 30. Throughout this protocol, a cutoff score of 23 or less shall prompt study staff to report the score to the treating physician for clinical decision-making.

5.5.2 Registration

Per UFHCC policy, patients must be registered into UF’s OnCore within one business day of consent. Status changes must also be updated within one business day.

Sites should notify the Coordinating Center by one of the following:

- Enter into eCRF (REDCap)
- Email to *[contact]*
- Fax to [contact] with phone confirmation to [contact]

A minimum amount of data is required for registration and status changes. CRFs will be provided to all sites via the eCRF.

6 STUDY INTERVENTION

6.1 Study Intervention(s) Administration

6.1.1 Study Intervention Description

6.1.1.1 Treatment Plans – Optune (TTFIELDS) + temozolomide

Patients will begin study treatment with temozolomide and TTFIELDS within 2 weeks of the baseline evaluation, and no later than 6 weeks from last dose of concomitant temozolomide or radiation therapy (the latter of the two). A minimum of 6 and a maximum of 12 cycles of adjuvant temozolomide will be given, depending on tolerability and toxicity.

6.1.1.2 Periodic Evaluation until Treatment Termination

Patients will be seen and examined before each cycle of temozolomide. After a maximum of 12 cycles of adjuvant temozolomide, patients will be seen every 8 weeks. Brain MRI and QoL assessments will be performed every 8 weeks following the baseline MRI for the first 2 years then every 3 months thereafter until second progression (when TTFIELDS treatment will be terminated).

Patients will undergo the following studies or review every month until treatment termination:

- Physical examination
- Neurological status and performance status (KPS)
- Blood exams
- Optune Compliance
- Record of Adverse Events, concomitant medications and steroid dose

Patients will undergo the following studies or review every 8 weeks +/- 7 days until treatment termination:

- Quality of Life Questionnaires (EORTC QLQ-C30/BN20, and MMSE)
- Contrast-enhanced MRI

Screening MRI should be done within 21 days of study treatment start. MRI of the brain will be performed routinely at baseline and again every 8 weeks +/- 7 days until treatment termination or second progression, whichever is first. In case of clinical progression, an MRI will be performed within 21 days.

All MRI scans should be performed with and without contrast.

The data collection for patients who remain on Optune (on-study treatment) and begin 2nd line therapy should include labs and visits adjusted as appropriate for the standard care of that patient's 2nd line therapy.

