Study Population: Patients with tissue-based diagnosis of high-risk Grade II or III astrocytomas, 18 years or older, of both genders after surgery or biopsy followed by radiation therapy with concurrent temozolomide.

Phase: 2

Description of Sites/Facilities Enrolling Participants: This study is being conducted in a consortium of 10-20 high volume brain tumor centers in the U.S.

Description of Study Intervention: Treatment with TTFields (Optune®) with Adjuvant Temozolomide: TT Fields are applied through surface transducer arrays placed directly on the shaved head. Temozolomide is available in either tablet or IV infusion.

Study Duration: 60 months: 36 months enrollment plus 24 months follow-up/study completion

Accrual Goal: 100 interventional subjects and up to 100 historical and contemporaneous control subjects

Participant Duration: 24 months (study treatment) plus follow-up until death or until the study is complete/terminates.

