
4) Optune therapy should start within two weeks of start of adjuvant temozolomide, but not more than 7 weeks from the end of temozolomide/RT and will be continuous throughout study. Compliance documentation will be obtained every 4 weeks +/- 7 days.
							

5) Every 3 months until death. The only data required during survival follow-up is DOD.
							

6) Biochemistry panel will include electrolytes, creatinine, bilirubin, liver enzymes.
							

7) Patients will begin treatment with temozolomide at 4 weeks (+14 days) from end of radiotherapy. Cycle 1 will be dosed at 150mg/m² daily for 5 consecutive days of a 28-day cycle.
							

Study Procedure:	Screening ≤14 days prior to Day 0	Day 0 : Begin TMZ Treatment	Week 4 (-3/+7 days) and every 4 weeks until treatment stop	Week 8 (±7 days) and every 8 weeks only until treatment stop	Progression	After Treatment Stop (Week 4 (+/- 7 days) from end of treatment)	Survival follow-up

8) Patients will begin treatment with temozolomide Cycle 2 and subsequent cycles every 4 weeks (-3/+7 days) at 200mg/m² PO daily for 5 consecutive days, if CTC hematologic toxicity for cycle 1 is grade < 1 and the CTC non-hematologic toxicity for cycle 1 is grade ≤ 2. If dose escalation is not appropriate, the dose should remain at 150 mg/m² PO daily for 5 consecutive days for Cycle 2 and onward.
							

9) Verification of tissue availability and location should be determined at screening visit. When available, formalin fixed and paraffin embedded (FFPE), pathology slides and/or frozen samples will be obtained for primary tumors and first recurrent tumors.
							

10) Labs to be completed within 3 days for pre-TMZ cycles. Screening and other labs are within the visit windows noted. Pregnancy Test required for WOCBP only at Screening.
							

11) DICOM images will be shipped to Beth Israel Deaconess Medical Center for electric field mapping analysis at baseline, first progression and second progression. Imaging performed between shipping time points should be included in the next shipment.
							

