Progression	
Defined by any of the following:
 
 ≥ 25% increase in sum of the products of perpendicular diameters of enhancing lesions compared with the smallest tumor measurement obtained either at baseline (if no decrease) or best response, on stable or increasing doses of corticosteroids*. The absolute increase in any dimension must be at least 5mm when calculating the products. Significant increase in T2/FLAIR non-enhancing lesion on stable or increasing doses of corticosteroids compared with baseline scan or best response after initiation of therapy* not caused by comorbid events (e.g. radiation therapy, demyelination, ischemic injury, infection, seizures, postoperative changes, or other treatment effects). Any new measureable lesion. Clear clinical deterioration not attributable to other causes apart from the tumor (e.g. seizures, medication adverse effects, complications of therapy, cerebrovascular events, infection, and so on) or changes in corticosteroid dose. Failure to return for evaluation as a result of death or deteriorating condition; or clear progression of non-measurable disease.

- All measurable and non-measurable lesions must be assessed using the same techniques as at baseline.

- Abbreviations: MRI, magnetic resonance imaging; FLAIR, fluid-attenuated inversion recovery.
- Stable doses of corticosteroids include patients not on corticosteroids.

The determination of whether to stop treatment due to progression will be based on the investigator's evaluation of the patient's clinical condition. TTFelds treatment will be continued for 24 months or until second progression whichever occurs first unless the patient's clinical condition prohibits this. In the case of radiological progression based on local evaluation, temozolomide treatment will be stopped and a second line treatment chosen instead. The following treatments or any combination of these treatments are considered second line therapy in this protocol:

- Re-operation
- Local radiation therapy
- Second line therapy
- Combination of the above

6.1.1.3.1.2 DISEASE PARAMETERS

Measurable disease: Bi-dimensionally measurable lesions with clearly defined margins by MRI scan. All tumor measurements must be recorded in millimeters (or decimal fractions of centimeters).

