6.1.2.5 Treatment after temozolomide discontinuation

Following temozolomide discontinuation due to toxicity or radiological disease progression (based on local interpretation of MRI), patients will be offered second line therapy for their disease. The following treatment options may be considered based on the patient's clinical condition per the treating physician's discretion:

1. Re-operation (TTFIELDS treatment will be interrupted for at least 2 weeks after reoperation or until wound healing is sufficient to resume).

2. Local radiation therapy
3. Second line therapy (at the discretion of the treating physician and not limited to traditional cytotoxic chemotherapy)
4. Combination of the above

TTF treatment will continue concomitant with second line treatments until second disease progression for TTFIELDS + temozolomide patients.

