6.1.2.6 Optune (TTFIELDS) + temozolomide

Optune treatment will be initiated in an outpatient clinic by the investigator's team at each center or at home by Novocure's device support specialists (DSS). 3D mapping of tumors using the FDA-approved NovoTAL software will be completed by a NovoTAL-certified treating physician or by Novocure. Scalp shaving, array placement and all device support services (including patients' and families' education of device operation, downloading and processing of technical and compliance data, and troubleshooting device malfunction) will be provided by the DSS for the first placement. Patients and/or their caregivers will continue treatment at home after being trained in device use with the support of DSS as needed.

TTFIELDS will start within 2 weeks of the first cycle of adjuvant temozolomide but must be within 7 weeks after end of temozolomide/RT. Adjuvant Temozolomide will continue for a minimum of 6 and a maximum of 12 cycles. Optune will continue for a maximum of 2 years. At first progression, patients will be allowed to continue with TTFIELDS therapy with any other therapy per standard of care. Patients will receive up to 12 one-month courses of continuous Optune treatment together with standard adjuvant temozolomide. The decision to add each additional treatment course will depend on the lack of treatment related serious adverse events which reappear upon re-challenge and lack of clinical disease progression. All technical aspects of the Optune device are handled by the DSS.

During Optune treatment the patient will be permitted to interrupt treatment for personal needs with the goal of achieving approximately 75% of the time over each 4-week period. Compliance reports with TTFIELDS will be obtained by Novocure's DSS per usual clinical treatment procedures. If a patient's compliance is below 75% of the time over any 4-week period, the patient will be trained on the importance of compliance and any barriers to compliance will be addressed by the DSS. If a patient's compliance is below 50% of the time over any 4-week period, the patient will be trained on the importance of compliance and any barriers to compliance will be addressed by the DSS and study staff.

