Approximately once per month, from baseline until treatment termination, all patients will report to an outpatient clinic where they will be assessed clinically and undergo routine laboratory examinations. The follow-up window for these visits is -3/+ 7 days for the Adjuvant TMZ follow-up window of approximately 12 months. The follow-up window after discontinuation of Adjuvant TMZ will be +/- 1 month. If patients are removed from study therapy due to toxicity and/or disease progression prior to the 2-year study treatment, the patients will have an end of study therapy visit within 1 month +/- 7 days. After this end of study therapy visit, patients will be followed by telephone interview every 3 months until death.

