6.1.2.6.1 RECOMMENDATIONS FOR USE OF OPTUNE

All patients treated with Optune will be required to shave their heads to initiate array placement and Optune therapy. Array placement will be performed based on the transducer array map calculated during treatment planning. It is recommended that treatment with the device be continuous with breaks allowed for personal needs (e.g., showering, array exchange). Breaks should be no more than 1 hour twice daily.

Use compliance is aimed at a minimum of 50% (12 hours) with the goal of achieving at least 75% (18 hours) of the time per day on average. In addition, investigators may grant brief breaks in device treatment that last no more than 3 days in any 30-day period at the investigator's discretion. Subjects should be counseled by study staff if compliance reports show less than 50% compliance.

Optune is programmed by Novocure to deliver 200 kHz TFields in two sequential, perpendicular field directions at a maximal intensity of 707 mARMS. There will be no adjustments made to the device by investigators or patients/caregivers.

It is recommended that patients replace the transducer arrays 2-3 times per week with the help of a caregiver. At each array replacement, it is recommended that the patient's scalp be re-shaved and skin treated according to the guidelines in section "Skin Care Guidelines."

There will be no dose adjustments to the device for adverse events. Reasons for breaks in treatment for longer than 24 hours will be documented.

Optune therapy will be stopped in the following cases:

- The occurrence of serious adverse events probably or definitely related to treatment with TFields
- Clinical and functional deterioration considered by the investigator to be prohibitive of continuing treatment.
- After 24 months or after second progression, whichever occurs first.

Treatment with the Optune does not need to be terminated in the following situations:

- Toxicity due to temozolomide treatment
- Radiological progression alone will not lead to termination of TFields treatment, but to replacement of the temozolomide treatment with best standard of care second line therapy:
 - Re-operation
 - Local radiation therapy
 - Second line therapy

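### The protocol caps TTFields at 24 months in some sections and runs it to second progression without a cap in others, so treatment and observation after month 24 are not defined

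*Combined protocol and SAP*

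**What the plan says.** **Sections that set a time limit**

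- Section 6.1.1.3.1.1 (after Table 4): TTFields "treatment will be continued for 24 months or until second progression whichever occurs first".
- Section 6.1.2.6.1 (list of reasons to stop Optune): "After 24 months or after second progression, whichever occurs first".
- Section 6.1.2.6: "Optune will continue for a maximum of 2 years". The same section later covers patients removed from therapy "prior to the 2-year study treatment".
- Section 1.1 (Synopsis): "Participant Duration: 24 months (study treatment) plus follow-up until death or until the study is complete/terminates". It gives the length of study treatment without naming the device.

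**Sections that set no time limit**

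- Section 6.1.1.2, under a heading about evaluation until treatment termination: MRI and quality of life every 8 weeks "for the first 2 years then every 3 months thereafter until second progression (when TTFIELDS treatment will be terminated".
- Section 6.1.2.5: "TTF treatment will continue concomitant with second line treatments until second disease progression for TTFIELDS + temozolomide patients".
- Section 1.3 (Table 1, footnote 4) and section 8.1: Optune "will be continuous throughout study". This is loose wording and only secondary evidence.

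**The concern.** The two groups of sections agree until month 24. From then on, a patient without second progression stops the device under one group and stays on it under the other. All of these sections are current operative text.

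The end of TTFields is also the switch for other schedules: monthly visits and compliance reports, the After Treatment Stop visit, adverse event recording, post-treatment MRI and telephone follow-up. The same patient could therefore be treated and observed differently at different sites among the 10 to 20 planned. The intervention under test would also not be one defined regimen after year 2.

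**Working it through.** **1. Can section 6.1.1.2 be read as shorthand for the cap?** No. It sets an interval for assessments after year 2 and names second progression as the point at which TTFields ends. Under a 24-month cap nobody would be on treatment in that period.

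**2. Is section 6.1.1.2 consistent with itself?** No. One sentence gives MRI and quality of life every 8 weeks for 2 years and then every 3 months. A later list in the same section gives both every 8 weeks until treatment termination. Table 1 footnote 1 also keeps MRI at 8 weeks until treatment termination or second progression.

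**3. Does Table 1 fit the cap?** Not for quality of life. Footnote 2 requires it every 3 months after the first 2 years. Table 1 marks it only at screening, in the 8-weekly column that ends at treatment stop, and at progression. Sections 6.1.1.3.2.6 and 8.2.1, which cover the period after treatment stop, do not list it. If treatment stops at month 24, the later assessments have no visit.

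**4. What differs after month 24 for a patient without second progression?**

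| Item | Device stops at month 24 | Device continues to second progression |
|---|---|---|
| Device exposure and compliance data (compliance–OS correlation, Table 2) | End at month 24 | Continue |
| AE/SAE recording (8.3.5) | Ends 30 days after the After Treatment Stop visit, itself 4 weeks after stop: 28 + 30 = 58 days, about month 26 | Ends about 58 days after the later stop |
| Quality of life | No scheduled visit | Every 3 months (or every 8 weeks, step 2) |
| Follow-up, first progression already occurred | Telephone only after the end-of-therapy visit (6.1.1.3.2.6) | MRI every 3 months to second progression |
| MRI, never progressed | Every 3 months for 12 months, then every 6 months for 24 months, then yearly | Every 3 months (or every 8 weeks, step 2) |

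On the 3-month line, the last row is nominally the same under both readings for about months 24 to 36 and differs only afterwards.

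**5. How many patients could be affected?** The plan gives no figure, so this step is for scale only.

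Inputs (sections 10.1 and 10.2): control median 22 months; improvements M of 4 to 8 months; Weibull shape k = 2.0 or 1.8; 90 device patients; 2.5 patients per month for 36 months; 24 further months of follow-up.

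*Model check.* HR = (22/(22+M))^k and power = Φ(|ln HR|·√(D/4) − 1.645). For 90+0 controls, k = 2.0 and M = 6, HR = (22/28)² = 0.617. With follow-up staggered over 24 to 60 months in both arms, expected deaths are 78.4 + 67.6 = 146.0. Power is 0.898, against 0.894 in Table 10. All ten cells for 90 historical controls (M = 4 to 8, both shapes) agree within 0.01. Giving every control a fixed 60 months yields 0.916 for that cell, so the staggered version is used.

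*Alive at month 24.* S(24) = 0.5^((24/median)^k).

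| M (median) | S(24), k = 2.0 | of 90 | S(24), k = 1.8 | of 90 |
|---|---|---|---|---|
| 0 (22) | 0.438 | 39.4 | 0.445 | 40.0 |
| 4 (26) | 0.554 | 49.9 | 0.549 | 49.4 |
| 6 (28) | 0.601 | 54.1 | 0.591 | 53.2 |
| 8 (30) | 0.642 | 57.8 | 0.629 | 56.6 |

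*Further time in the study.* For entry time a uniform on 0 to 36 months, integrate S(t) from 24 to 60 − a, average over a, and divide by S(24). The result is 9.6 to 11.4 months per 24-month survivor for M = 4 to 8, and 8.0 to 8.8 months for M = 0. The maximum, 60 − 24 = 36 months, applies only to the earliest enrollee.

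**6. Table 11.** Section 10.4 describes the consequence of crossing the boundary as a halt in enrolment. Accrual lasts 36 months, so only patients enrolled in the first 36 − 24 = 12 months can pass month 24 while it is open. That is 2.5 × 12 = 30 patients, of whom about 13 to 19 would be alive at month 24 (30 × 0.438 to 30 × 0.642).

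**The case against.** The strongest reply is that the cap is stated repeatedly, including in the list of reasons to stop Optune, and that the remaining wording is incidental.

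Part of this stands. The phrase about continuous use in Table 1 footnote 4 and section 8.1 most naturally describes how the device is worn. Taken literally it would override the second-progression stop as well, so it is not a competing end rule. Section 6.1.2.5 deals with what follows temozolomide discontinuation and is silent on the cap rather than denying it. Section 6.1.1.2 also has a sentence that treats treatment termination and second progression as separate events. The reply fails for the post-year-2 schedule in section 6.1.1.2 and for Table 1 footnote 2, neither of which fits a 24-month stop.

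A reader might infer more than the documents support:

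- **That the primary analysis is compromised.** OS is followed to death under either reading, and nothing in Table 10 depends on device duration.
- **That PFS is broadly affected.** Patients past first progression already have their PFS event, and second progression is not an endpoint. Only late dates in never-progressed patients could shift, from about month 36 on the 3-month line.
- **That the number of patients whose treatment end is undefined can be estimated.** The documents give no rate of second progression or early device stop, so only an upper bound is available.
- **That exposure typically differs by 36 months, or that Table 11 monitoring is generally undermined.** Steps 5 and 6 show how narrow both are.

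**Conclusion.** Wrong as written: an internal contradiction on when TTFields ends, with schedules that cannot all be followed after month 24. It concerns at most about 39 to 58 of 90 device patients. The lower end assumes no benefit, the upper end an 8-month gain in median OS, and both rest on the plan's Weibull model. The true number is smaller to the extent that patients have had a second progression or stopped the device earlier.

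The consequences are confined to device exposure and its correlation with OS, the safety window, quality of life after year 2, imaging against telephone follow-up for patients past first progression, and late MRI frequency for those never progressed. Sample size and power need no recalculation.

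**What to change.** Reconcile sections 6.1.1.2 and 6.1.2.5 with sections 1.1, 6.1.1.3.1.1, 6.1.2.6 and 6.1.2.6.1 so that one TTFields end rule appears everywhere. Tidy the wording in Table 1 footnote 4 and section 8.1 to match. Then align the MRI, quality of life, visit and AE schedules for patients who reach month 24 without second progression. This includes a single on-treatment interval in section 6.1.1.2 and, if quality of life is wanted after year 2, a column for it in Table 1. Which duration applies is for the sponsor to decide.

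The cost is a protocol wording amendment. The reconciliation itself adds no patients; the number of visits and scans after month 24 follows from the rule chosen.
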